9.5 Local Tolerability Assessments

Local tolerability assessments are performed for both axillae individually at all visits after screening (Visits 2-17). Visit 2 data are the baseline. Should Visit 2 data be missing, baseline will be derived as the last value prior to first dose and as such unscheduled visits may be included. Subjects rate the severity of any symptoms of burning, stinging, and itching at the application-site on a scale of 0 = absent, 1 = minimal, 2 = mild, 3 = moderate, and 4 = severe. Investigators assess the drug application site for the existence of significant local symptoms of scaling and erythema on a scale of 0 = absent, 1 = minimal, 2 = mild, 3 = moderate, and 4 = severe.

Subject and Investigator assessments will be included in tables and listings. At each visit, local tolerability assessments will be descriptively summarized by severity for each treatment group. At each post-baseline visit, local tolerability will be summarized as cumulative shift tables vs. baseline. Subject counts and percentages for each symptom will be cross-tabulated with baseline severity according to the maximum post-baseline severity reported for either axilla up to the current visit.

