8.1.2 Adverse Events

Adverse events (AEs; See Section 9.2) will be collected for all untoward medical occurrences in a subject entered into this clinical study (e.g., signed consent), whether or not a pharmaceutical product has been administered. Any event, including local tolerability assessments (see Section 8.1.3), that requires specific treatment, results in interruption of treatment, or results in discontinuation of the subject from the study will also be reported as an AE.

Care will be taken not to introduce bias when detecting AEs and/or SAEs. Open-ended and non-leading verbal questioning of the subject is the preferred method to inquire about AE occurrence.

Appropriate questions include:

- "How are you feeling?"
- "Have you had any (other) medical problems since your last visit/contact?"
- "Have you taken any new medicines, other than those provided in this study, since your last visit/contact?"

8.1.3 *Local Tolerability Assessments*

Local tolerability assessments (See Appendix 4) will be evaluated through assessment of selected local signs and symptoms at the drug-application site. Burning, itching, dryness, scaling and erythema will be assessed using standardized 5-point scales (0-Absent to 4-Severe). These assessments are to be performed for both axillae individually. Subject assessments (burning and itching) will be made prior to the Investigator assessments (dryness, scaling and erythema).

Subject Local Tolerability Assessments: Burning and itching for each axilla will be reviewed with the subject and assessed for the previous 24 hours using the standardized scales.

Investigator Local Tolerability Assessments: Dryness, scaling, and erythema for each axilla will be assessed by the Investigator using the standardized scales.

Local tolerability signs and symptoms that result in the subject's requiring a concomitant therapy, interruption of treatment, or discontinuation from the study, will be reported as an AE.

8.1.4 *Recommendations for Dose Interruption*

To manage AEs, the Investigator may consider interruption of treatment, and/or the use of concomitant therapy. Recommended concomitant therapy includes topically applied corticosteroids. Recommendations for dose interruption are described in the table below:

Recommended Dose Interruption

Dose Interruption		
First Dose InterruptionHold treatment until the adverse event has resolved. Result dosing.		

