10.1 Analysis Populations

Subjects will be classified into the Safety, Intent-to-Treat (ITT), and Per-Protocol (PP) patient sets according to the following definitions.

Safety Patient Set

The Safety Patient Set will include all subjects randomized in the study who received study drug at least once. Subjects will be included in the treatment group based on the majority of actual treatment they received (even if not the treatment group to which they were randomized).

ITT Population

The ITT Patient Set will include all subjects who were randomized and dispensed study drug. Subjects will be included in the treatment group to which they were randomized, regardless of the treatment received.

PP Population

The PP Patient Set will be a subset of the ITT Patient Set and will include subjects who meet the following criteria:

- Meets the inclusion/exclusion criteria
- Has not taken or applied any interfering concomitant medications.
- Completed the following visits:
 - Visit 1 (Screening) and the required data collection
 - Visit 2 (Baseline) and the required data collection
 - Visit 4 (Week 4), and the required data collection
 - Visit 7 (Week 12), and the required data collection
 - Visit 10 (Week 24), and the required data collection
 - Visit 16 (Week 48), and the required data collection
 - Visit 17 (Week 52), and the required data collection
- Required treatment received per randomization

10.2 **Endpoints**

Primary endpoints include evaluation of the long-term safety and local tolerability of 5% and 15% sofpironium bromide gel when applied topically in subjects with axillary hyperhidrosis. Assessment will include:

- Adverse events
- Local tolerability assessments including burning, itching, dryness, scaling, and erythema
- Vital signs (blood pressure, pulse rate, respiratory rate, and temperature)
- Laboratory tests (hematology, chemistry, and urinalysis) and pregnancy testing in FOCBP

Secondary endpoints - Efficacy:

Definitions

"Baseline" HDSM-Ax = Visit 2 (Week 2) assessment

"End of treatment" HDSM-Ax = Visit 16 (Week 48) assessment

Efficacy Endpoints

- 1. The proportion of subjects achieving \geq 1-point improvement in HDSM-Ax from baseline to end of treatment
- 2. The proportion of subjects achieving \geq 1.5-point improvement in HDSM-Ax from baseline to end of treatment
- 3. The proportion of subjects achieving \geq 2-point improvement in HDSM-Ax from baseline to end of treatment

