APPENDIX 4: TOLERABILITY ASSESSMENTS

These assessments are to be performed for each axilla individually. The designation of "Right Axilla" or "Left Axilla" in the source documents and e-CRFs refers to the subject's right and left axilla respectively in all cases. Subject assessments are to be performed prior to Investigator assessments.

Local Tolerability (Subject): The severity of burning and itching of the axilla as reported by the Subject to the Investigator:

Score	Burning	Itching
0 = Absent	Normal, no discomfort	Normal, no discomfort
1 = Minimal	An awareness, but no discomfort	An awareness, but no discomfort
2 = Mild	Noticeable discomfort causing intermittent awareness	Noticeable discomfort causing intermittent awareness
3 = Moderate	Noticeable discomfort causing continuous awareness	Noticeable discomfort causing continuous awareness
4 = Severe	Definite discomfort causing continuous awareness, interfering occasionally with normal daily activities	Definite discomfort causing continuous awareness, interfering occasionally with normal daily activities

Local tolerability (Investigator): The Investigator will grade the severity of dryness, scaling, and erythema on each axilla as observed:

Score	Dryness	Scaling	Erythema
0 = Absent	None	No scaling	No redness
1 = Minimal	Barely perceptible dryness by palpation with no accentuation of skin markings, skin desquamation (flakes), or fissure formation	Fine scaling, barely perceptible	Faint red or pink coloration, barely perceptible
2 = Mild	Easily perceptible dryness by palpation with accentuation of skin markings but no skin desquamation (flakes) or fissure formation	Slight scaling, noticeable only with light scratching	Light red or pink coloration
3 = Moderate	Easily noted dryness with accentuation of skin markings and skin desquamation (small flakes) but no fissure formation	Definitely noticeable scaling	Medium red coloration
4 = Severe	Easily noted dryness with accentuation of skin markings, skin desquamation (large flakes), and/or fissure formation	Extensive scaling	Beet red coloration

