	Adverse Events of Special Interest Cumulative to Week 52 by	Reaching Week
14.3.1.10.13	System Organ Class, Preferred Term, and Maximum Severity	52)
		Safety (All Safety
	Number and Percentage of Subjects with Treatment-Emergent	Subjects,
	Adverse Events of Special Interest Cumulative to Week 52 by	Reaching Week 52
14.3.1.10.14	System Organ Class, Preferred Term, and Maximum Severity	or Not)

Version: 1.0 Page 45 of 51

	Number and Percentage of Subjects with Anticholinergic		
	Treatment-Emergent Adverse Events Cumulative to Week 52	Safety (Subjects	
	by System Organ Class, Preferred Term, and Maximum	Reaching Week	
14.3.1.10.15	Severity	52)	
	Number and Percentage of Subjects with Anticholinergic	Safety (All Safety	
	Treatment-Emergent Adverse Events Cumulative to Week 52	Subjects,	
	by System Organ Class, Preferred Term, and Maximum	Reaching Week 52	
14.3.1.10.16	Severity	or Not)	
	Worst Post-baseline Severity for Local Tolerability	,	
14.3.6.1	Assessments by Treatment Group	Safety	
	Worst Severity for Local Tolerability Assessments by		
14.3.6.2	Treatment Group and Visit	Safety	
14.3.6.3	Summary of Vital Signs	Safety	
	Mean and Mean Change from Baseline in Serum		
14.3.4.1	Biochemistry Values by Visit	Safety	
	Mean and Mean Change from Baseline in Hematology Values		
14.3.4.2	by Visit	Safety	
	Mean and Mean Change from Baseline in Continuous		
14.3.4.3	Urinalysis Values by Visit	Safety	
14.3.4.4	Categorical Urinalysis Values by Visit	Safety	
	Shift in Serum Biochemistry Results from Baseline to Each		
14.3.4.5	Visit	Safety	
14.3.4.6	Shift in Hematology Results from Baseline to Each Visit	Safety	
	Shift in Continuous Urinalysis Results from Baseline to Each		
14.3.4.7	Visit	Safety	
	Shift in Categorical Urinalysis Results from Baseline to Each		
14.3.4.8	Visit	Safety	
14.3.5	Study Drug Administration Exposure and Compliance	Safety	
	Summary of Concomitant Medications by Drug Class and		
14.3.6.4	Generic Drug Name	Safety	

Version: 1.0 Page 46 of 51

16.LIST OF PLANNED FIGURES

Number	Description	Analysis Set
	Proportion of Subjects Achieving ≥1-point	
14.2.1.1.1	Improvement in HDSM-Ax-11 by Visit	ITT
	Proportion of Subjects Achieving ≥1-point	
14.2.1.1.2	Improvement in HDSM-Ax-11 by Visit	Per Protocol
	Proportion of Subjects Achieving ≥1.5-point	
14.2.1.2.1	Improvement in HDSM-Ax-11 by Visit	ITT
	Proportion of Subjects Achieving ≥1.5-point	
14.2.1.2.2	Improvement in HDSM-Ax-11 by Visit	Per Protocol
	Proportion of Subjects Achieving ≥2-point	

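### The tolerability items in SAP 9.5 differ from the supplied protocol (no dryness, stinging added) without explanation, and the SAP's table list names no tolerability shift table although 9.5 requires one

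*SAP*

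**What the plan says.** The supplied protocol is Amendment 01, dated 15 May 2018. Its Section 10.2 (Endpoints) lists among the primary endpoints "Local tolerability assessments including burning, itching, dryness, scaling, and erythema". Section 8.1.3 divides the work between raters: "Subject assessments (burning and itching) will be made prior to the Investigator assessments (dryness, scaling and erythema". It adds that "Dryness, scaling, and erythema for each axilla will be assessed by the Investigator". Appendix 4 gives dryness its own 0 to 4 scale, introduced by "The Investigator will grade the severity of dryness, scaling, and erythema on each axilla as observed". It has no scale for stinging.

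SAP 9.5 (Local Tolerability Assessments) has a different list. For the subject: "Subjects rate the severity of any symptoms of burning, stinging, and itching". For the investigator: "Investigators assess the drug application site for the existence of significant local symptoms of scaling and erythema". Baseline is Visit 2 or, if that is missing, the last value before the first dose. For the analysis, 9.5 says: "At each post-baseline visit, local tolerability will be summarized as cumulative shift tables vs. baseline". Baseline severity is to be crossed with the worst severity in either axilla up to the visit in question.

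SAP Section 15 (List of Planned Tables) has two tolerability tables. Table 14.3.6.1 is headed "Worst Post-baseline Severity for Local Tolerability" and is presented by treatment group. Table 14.3.6.2 gives worst severity by treatment group and visit.

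SAP Section 1 bases the plan on protocol Amendment 4 of 6 May 2019. Section 13 lists the changes from that version, and none concerns tolerability.

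**The concern.** Local tolerability is half of the primary objective. Dryness is one of the five signs and symptoms by which the supplied protocol measures it, and one of three that the investigator rates. A programmer who followed SAP 9.5 to the letter would summarise stinging and not dryness, and nothing in the SAP says why.

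The shift tables matter because both arms receive active gel, the study is open-label, and there is no vehicle group. Crossing baseline severity with the worst severity on treatment is the planned way to separate signs already present from signs that arise during treatment. If that table is not on the list of outputs, it may not be produced.

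**Working it through.** No arithmetic from a sample size, rate or test enters here; the SAP states that no formal sample size calculation was done (2.6) and plans no hypothesis tests (3.1). The check is a comparison of texts.

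**Step 1: the items.**

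| Item | Protocol Amendment 01 (8.1.3, 10.2, 10.3, Appendix 4) | SAP 9.5 |
|---|---|---|
| Burning | subject | subject |
| Itching | subject | subject |
| Stinging | not named | subject |
| Dryness | investigator | not named |
| Scaling | investigator | investigator |
| Erythema | investigator | investigator |

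Each list has 5 items and 4 are shared. Relative to Amendment 01 the SAP leaves out 1 of 5 items (1 of 3 investigator-rated) and adds 1. Subject-rated items go from 2 to 3; investigator-rated items go from 3 to 2.

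**Step 2: is the difference explained?** SAP Section 13 covers the HDSM-Ax baseline, the ITT definition, the HidroQoL interim look, added HDSM-Ax endpoints and the adverse event tables. It does not mention tolerability. But it records departures from Amendment 4 only, so its silence settles nothing about Amendment 01. Three cases remain:

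- Amendment 4 still has dryness. SAP 9.5 then departs from a primary-endpoint component and Section 13 fails to record it.
- An amendment replaced dryness with stinging after some subjects had been scored. Those subjects have dryness scores that 9.5 does not tabulate. If they were dosed before stinging was introduced, they also have no stinging baseline. The 9.5 fallback, the last value before dosing, cannot supply one, so they would fall out of any stinging shift table.
- The scale changed before anyone was scored. The question of items is then moot, but neither document says so.

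**Step 3: what would happen to dryness scores, if collected?** SAP 3.1 requires all data collected per protocol to be listed, and Listing 16.2.9.1 covers local tolerability. They would therefore appear by subject, but in no summary table that 9.5 specifies.

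**Step 4: the table list against 9.5.** Titles in Section 15 that contain the word Shift:

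- PGI-S: 14.2.2.15.1 and 14.2.2.15.2 (2)
- Laboratory: 14.3.4.5 to 14.3.4.8 (4)
- Local tolerability: 0 of 2

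That makes 2 + 4 = 6 titled shift tables, none for tolerability. The title of 14.3.6.1 mentions no visit, and that of 14.3.6.2 mentions no baseline. The table in 9.5 needs both, at each of Visits 3 to 17, which is 15 post-baseline visits. This gap lies within the SAP and does not depend on which protocol version governs.

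**The case against.** The strongest reply is that the SAP follows Amendment 4, which the documents do not include, and that Amendment 4 may itself have changed the items. There are signs of that. SAP 2.2.1, 2.3 and 9.2 refer to local tolerability without the bracketed or trailing list that the protocol carries in the matching places. Other content plainly moved between versions: the minimum age is 9 rather than 12, and the SAP has a child HDSM-Ax scale and an optional end-of-study survey. A reader might infer from the two lists that the SAP contradicts its governing protocol. The documents do not support that; they show only a difference from Amendment 01.

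The opposite inference is no safer. The SAP has slips of its own: 8.1.4 places PGI-C at a Day 43 visit, while 8.2.1 and the schedule have Weeks 24 and 48; 9.6 has laboratory results at Visits 3 to 16, while the schedule has Screening and Weeks 6, 24 and 48. A drafting error in 9.5 is therefore a live explanation.

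Three further replies stand:

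- A reader might conclude that dryness data would be lost. They would not: they would be listed, and under protocol 8.1.3 any sign that needs concomitant therapy, interruption or discontinuation is also reported as an adverse event. SAP 3.1 also bases percentages on available data and shows missing counts, which partly covers an item scored in only some subjects.
- A reader might conclude that the shift analysis has been dropped. The text of 9.5 still requires it. The table specifications are in a separate document, and 14.3.6.1 may carry the cross-tabulation. What is shown is a disagreement between 9.5 and the titles in Section 15.
- A reader might argue from the dates of the SAP and Amendment 4 that some subjects must have been scored on the Amendment 01 scale. The documents give neither enrolment dates nor the version in which the scale changed, if it did. The number affected could be anything from none to all.

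**Conclusion.** The point holds in two parts, both modest and both worth correcting before the tables are run.

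First, SAP 9.5 and the supplied protocol share 4 of 5 tolerability items. Dryness is missing from the SAP, stinging is added, and no reason is given. Without Amendment 4 one cannot say whether this is an unrecorded departure or a change of scale that 9.5 does not handle. In either case any dryness scores collected would be listed but not tabulated. The part falls away only if the scale changed before anyone was scored, which neither document shows.

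Second, 9.5 requires a cumulative shift table by visit and Section 15 lists none under that description. This rests on the table titles alone, since the shells are not available.

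All analyses are descriptive, so no test or error rate is affected. What is at stake is whether the summary of a primary endpoint is complete and can be traced to the protocol.

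**What to change.** 1. Check the tolerability items against Amendment 4 and the CRF.
2. In SAP 9.5, tabulate every item collected: burning, itching, scaling and erythema; dryness wherever it was scored; and stinging from the protocol version that introduced it. Show the number assessed at baseline and at each visit, so that a partly collected item is visible as such.
3. State in the SAP any change of scale between protocol versions. If 9.5 departs from Amendment 4, list that in Section 13.
4. Add to Section 15, for each item, a table such as *Cumulative shift from baseline in local tolerability by visit*, or retitle the existing table if its shell already contains the cross-tabulation.

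The cost is some SAP wording and a few more descriptive tables: five shift tables, or six if both dryness and stinging were collected. No new data and no change to the conduct of the study are needed, and the fix is sound whichever explanation proves right.

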9.6 Clinical Laboratory Evaluation

Laboratory parameter results will be collected at the Screening Visit and Visits 3-16. Baseline will be derived as the last value prior to first dose and as such unscheduled visits may be included.

Laboratory parameters will be presented in Systeme International (SI) units and descriptively summarized for values at each visit and for changes from baseline at each

Version: 1.0 Page 27 of 51

subsequent visit. In addition, at each post-baseline visit, parameter status (low, normal, high or normal, abnormal, as applicable) will also be summarized as shift tables vs. baseline status. Summary results will include the count and percentage of subjects within each shift category and treatment group. Unscheduled visits and early termination visits will be included in the shift tables.

Laboratory parameters to be summarized and listed include hematology, clinical chemistry, and routine urinalysis. Urine pregnancy test results will be a by-subject listing only. Laboratory measurements identified as abnormal (i.e., outside the normal range) will also be listed separately by subject, laboratory test, and unit.

9.7 Vital Signs, Physical Findings, and Other Observations Related to Safety

9.7.1 Vital Signs

Vital sign results will be collected at each visit. Visit 2 data are the Baseline. Should Visit 2 data be missing, baseline will be derived as the last value prior to first dose and as such unscheduled visits may be included. Vital sign measurements will include systolic and diastolic blood pressure, pulse rate, respiratory rate, and temperature. Vital sign parameters will be summarized with descriptive statistics for values at each visit and for changes from baseline at each subsequent visit. Vital signs will also be listed by subject.

9.7.2 Physical Examinations (PE)

Physical examination results will be collected at the Screening Visit and End of Study Visit. Physical examination will include assessments of the head, eyes, ears, nose, throat, skin, thyroid, neurological, lungs, cardiovascular, abdomen (liver and spleen), lymph nodes, and extremities. Height and weight will also be measured and recorded. Results of the physical examination will be presented in subject data listings by subject, study visit, and body system.

9.7.3 Other Safety Measures

9.7.3.1 Prior and Concomitant Medications

Medications will be coded using the latest version of the WHO drug dictionary. Medications entered on the CRF will be mapped to ATC drug class (level 4) and drug name.

Prior and concomitant medications will be summarized separately and the study phase of each medication will be determined programmatically based on medication start and end dates. Partial or missing start and end dates will be imputed according to Section 9.1.1.

A prior medication is defined as any medication administered prior to the date of the first dose of study drug. A concomitant medication is defined as any medication administered

Version: 1.0 Page 28 of 51

Statistical Analysis Plan 24 February 2020

on or after the date of the first dose of study drug. A medication may be defined as both prior and concomitant.

For the summary of both prior medications and concomitant medications, the number and percentage of subjects receiving any medication will be summarized by treatment group, as will the number and percentage receiving any medication by ATC drug class and generic drug name. Subjects reporting use of more than one medication at each level of summarization (any medication received, ATC class, and generic drug name) will be counted only once. ATC class terms will be displayed by descending order of incidence, as will generic drug names within each ATC class. The study phase during which each medication was received (e.g., prior, concomitant, or both) will be presented on the listing of prior and concomitant medications.

Prior or concomitant therapies and procedures will be listed only.

Version: 1.0 Page 29 of 51

Statistical Analysis Plan 24 February 2020

10. PHARMACOKINETIC/PHARMACODYNAMIC EVALUATION

Pharmacokinetic and pharmacodynamic analyses are not part of this study protocol.

Version: 1.0 Page 30 of 51

11. OTHER ANALYSES

11.1 Psychometric Analysis of the HDSM-Ax

In parallel to the traditional statistical analysis, psychometric evaluation of the HDSM-Ax will be carried out to confirm the most appropriate HDSM-Ax scoring algorithm and to examine internal validity, construct validity (i.e., examination of the magnitude of correlation between the HDSM-Ax total score and key variable such as items 4 and 5 of the HDSM-Ax, PGI-S, and PGI-C), stability, reliability, ability to detect change, and interpretability of clinical trial results.

The details regarding psychometric analyses will be described in a separate analysis plan.

Version: 1.0 Page 31 of 51

Brickell Biotech, Inc. Protocol No. BBI-4000-CL-303

